14.3 Efficacy

14.3.1 Efficacy analysis population

The Efficacy Analysis Population will include all patients who receive ≥ 1 cycle of BGB324 and undergo a post-treatment assessment of response.

Patients who on review do not meet the protocol inclusion/exclusion criteria or have a major protocol deviation may be excluded from the efficacy analysis. This will be reviewed on a per patient basis at the pre-database lock meeting.

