3.2.1 Objective Response Rate (ORR)

Patients included in the study must be assessed for response to treatment, Overall Response (OR) determined by Investigator based on appropriate radiographic imaging and consistent with RECIST 1.1.

Each patient will be assigned to one of the following ordered categories for OR (from best to worst responses): Complete response (CR), Partial response (PR), Stable disease (SD), Progressive disease, Not Evaluable (NE) or Not Applicable at each timepoint.

The Best Overall Response (BOR) is determined once all the data for the patient is known and is defined as the best overall response recorded from the initiation of treatment until disease progression or date of subsequent therapy across all tumour assessment.

ORR defined as percentage of patients with a BOR assessed as CR or PR, i.e. patients with response, divided by the number of patients in efficacy population.

The one-sided, within-group tests of proportion of responders, against the null hypothesis of a response rate $\leq 5\%$ (this being the observed response rate under current treatment). Values of $p < 0.2$ will be taken as sufficient evidence of a trend to justify further study.

For analysis of the ORR, summary tables will be generated, presenting the number and percentage of responders (i.e. patients with CR or PR) and non-responders in efficacy population.

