4.5.3 Efficacy Population

The Efficacy Population will include all patients who receive ≥ 1 cycle of BGB324 and undergo an assessment of response post-baseline.

Patients who on review do not meet the protocol inclusion/exclusion criteria or have a major protocol deviation may be excluded from the efficacy analysis. This will be reviewed (and documented) on a per patient basis at the pre-database lock meeting.

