4.8 Blinding

This is an open-label study and consequently there are no blinding procedures in operation.

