5.11 Protocol Deviations

Deviations from the protocol will be documented on an ongoing basis by the study monitors and project manager throughout the study period.

At the time of database lock, prior to unblinding and while the protocol deviations are being reviewed, the project manager will forward all relevant documentation highlighting protocol deviations to the study statistician. These deviations will be included in the protocol violation document for agreement and will be listed with the protocol violations in the CSR.

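### Optional, case-by-case exclusions from the efficacy population can be decided with response known, and no planned table gives the Arm B response rate without them

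*SAP*

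**What the plan says.** The Efficacy Population (SAP 4.5.3, Protocol 14.3.1) requires at least one cycle of BGB324 and a response assessment on treatment. A further clause then allows removals. In the SAP: "Patients who on review do not meet the protocol inclusion/exclusion criteria or have a major protocol deviation may be excluded from the efficacy analysis". In the protocol: "have a major protocol deviation may be excluded from the efficacy analysis". Both leave the decision to be made "on a per patient basis at the pre-database lock meeting"; the SAP adds that it is documented.

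This population feeds the formal test. SAP 3.2.1 defines the ORR as responders "divided by the number of patients in efficacy population", SAP 5.1 runs efficacy analyses on it, and SAP 5.7.3.1 applies a one-sided binomial test at 0.2 in Arm B against a null of at most 5%. Response is "Overall Response (OR) determined by Investigator based on appropriate radiographic imaging".

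On blinding, SAP 4.8 says: "This is an open-label study and consequently there are no blinding procedures in operation". SAP 5.11 nevertheless has deviation documents passed to the statistician at database lock, "prior to unblinding and while the protocol deviations are being reviewed".

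**The concern.** Three features combine:

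- Exclusion is permitted rather than required, so two patients with the same deviation can be treated differently.
- The main trigger is undefined. Neither document says what makes a deviation major, and the planned outputs speak of important violations (Table 14.1.1.2) and important deviations (Listing 16.2.2.1) instead. Eligibility can also be read in more than one way. Protocol 9.1.4 criterion 12 accepts a blood test or a biopsy for negative T790M status, while Protocol 10.2.11 asks for biopsy confirmation of a negative blood result. Those sections need to be reconciled.
- The decision comes when responses are known or knowable. Protocol 14 places lock after all data are reconciled, and nothing keeps those at the meeting from seeing response data. The words about unblinding in SAP 5.11 give no protection, because nothing is blinded.

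At stake are the Arm B ORR, its confidence interval and the p<0.2 result, which the plan treats as enough of a trend to justify further study. Every planned efficacy table and figure (SAP 6.1.2 and 6.3) uses the Efficacy Population, so none shows the ORR with the excluded patients counted.

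**Working it through.** **Inputs.** Null rate 5%, one-sided level 0.2, binomial test (SAP 5.7.3.1). Arm B has 9 + 16 = 25 patients, with rejection at 4 or more responses in 25 and an alternative rate of 20% (SAP 4.9, Protocol 14.6). The documents give no expected number of exclusions, so 0 to 10 dropped non-responders were examined as an assumption.

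**The plan's own figures.** SAP 4.9 prints a type I error of at most 0.73 and power of at least 0.0367. Rejecting at 4 or more of 25 in a single stage gives P(X≥4 | 25, 0.05) = 0.0341 and P(X≥4 | 25, 0.20) = 0.7660.

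For the two-stage version, sum over stage 1 responses x: P(X₁=x) × c(x) × P(X₂≥4−x), with 9 and 16 patients. Here c(x)=1 for x≥1 and c(0)=1−(1−q)^9, where q is the stable-disease probability among non-responders.

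| q | Type I error | Power |
|---|---|---|
| 0 | 0.0297 | 0.7121 |
| uniform on (0,1) | 0.0336 | 0.7606 |
| 1 | 0.0341 | 0.7660 |

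The printed pair does not reproduce as labelled. If the labels were interchanged, 0.73 would be a plausible power, but 0.0367 would still exceed the largest type I error above. That is a separate matter and does not affect this point.

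**P-values after exclusions.** For k responders among n patients, p = P(X≥k | n, 0.05). For k=2 this is 1 − 0.95^n − n × 0.05 × 0.95^(n−1).

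| Responders/patients | ORR | p | p<0.2? |
|---|---|---|---|
| 3/25 | 12.0% | 0.1271 | yes |
| 2/24 | 8.3% | 0.3392 | no |
| 3/20 | 15.0% | 0.0755 | yes |
| 2/25 | 8.0% | 0.3576 | no |
| 2/20 | 10.0% | 0.2642 | no |
| 2/17 | 11.8% | 0.2078 | no |
| 2/16 | 12.5% | 0.1892 | yes |
| 4/25 | 16.0% | 0.0341 | yes |
| 4/20 | 20.0% | 0.0159 | yes |

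**Losing a pass.** One excluded responder takes 3/25 to 2/24. Exactly three responders in 25 has probability 0.1271 − 0.0341 = 0.0930 at a 5% rate and 0.9018 − 0.7660 = 0.1358 at 20%, where 0.9018 = P(X≥3 | 25, 0.20).

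**Gaining a pass.** With two responders, n must fall to 16, which is 25 − 16 = 9 dropped non-responders, or 9/25 = 36% of the arm. If the one-cycle and assessment requirements have already reduced the set to 17, one more is enough. Starting from 25, with non-responders dropped whenever it helps, the threshold stays at three responders and type I error at 0.1271 for up to eight drops. With nine or ten available, the threshold falls to two and type I error becomes P(X≥2 | 25, 0.05) = 0.3576, above the nominal 0.2.

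**Under the count rule.** SAP 4.9 requires four or more responses in 25, which conflicts with p<0.2 (met at three). Under it 3/25 has already failed, so the one-patient reversal above does not arise, and dropping non-responders leaves the count unchanged. The plan does not say how this rule applies to fewer than 25 patients.

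**The case against.** The best case for the plan is that exclusions are open to inspection and the stakes are low.

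- SAP 4.5.3 requires each decision to be documented before lock, and SAP 5.11 has deviations recorded throughout the study. Table 14.1.1.2 and Listings 16.2.1.3, 16.2.2.1 and 16.2.3 show violations, unmet criteria, deviations and the subjects excluded from analysis sets.
- The tumour and response listings (16.2.6.1 to 16.2.6.4) are on the Safety Population, so an excluded patient's response is still reported and a reader could rebuild the all-treated rate.
- Arm B's primary objective is safety, analysed on the Safety Population. Efficacy is secondary and described as essentially exploratory.

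All of this stands. A reader might infer that patients could vanish without trace, or that the reference to unblinding is the only safeguard; the listings show otherwise. A reader might also infer that any treated and scanned patient can be removed at will. The clause does not go that far: a patient must first fail a numbered criterion or be judged to have a major deviation.

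What remains is that visibility does not constrain the choice. A listing from which the rate can be recalculated is not a planned result.

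**Conclusion.** The concern holds as a modest weakness worth correcting. Exclusion is optional, rests partly on an undefined term and can be made with response known. The population it produces is the denominator of the only formal efficacy test.

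A reader might infer that the clause makes a false positive easy. The figures do not support that: from 25 patients it takes nine excluded non-responders, each with a qualifying failure or deviation, and nothing in the documents suggests such a rate. Going from 4/25 to 4/20 raises the estimate to the design alternative but changes no decision. The reversal that needs only one patient from a full arm removes a responder, makes the drug look worse, and exists only under the p<0.2 rule.

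Nor does the point carry equal weight for time to progression, which SAP 5.7.3.2 analyses in Arm C only and descriptively.

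The size rests on exact binomial tests against 5%, a full Arm B of 25 unless stated, and assumed numbers of exclusions.

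**What to change.** For the Arm B ORR test, do not exclude patients from the main analysis for eligibility failures or protocol deviations. Report such exclusions only in one labelled sensitivity analysis, with the disqualifying deviations listed in the SAP now and defined from entry and dosing data alone. Delete the reference to unblinding from SAP 5.11. The one-cycle and assessment requirements are a separate question and are untouched by this change.

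A lighter alternative is to keep the planned population and add an ORR table for all treated Arm B patients. That would show the effect of exclusions but leave the outcome-aware choice in the main result.

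The cost is SAP wording, one extra table and a matching edit to Protocol 14.3.1. The protocol edit is either an amendment, which Protocol 16.5.2 requires to be submitted to the IRB and Regulatory Authorities, or a departure recorded in SAP 5.14, which currently reports none. The headline ORR may shift slightly in either direction. Sample size and patient care are unaffected.

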4.6 Withdrawn Subjects

Patients may withdraw informed consent and discontinue from the study at any time, or for any reason, without prejudice to their future treatment.

The reason for the patient's withdrawal from the study must be recorded in the eCRF.

A patient must be discontinued from the study if any of the following criteria are met:

- Patient non-compliance with the protocol, as agreed by the Investigator and the Sponsor.
- Patient lost to follow-up.
- Termination of the study by the Sponsor.
- Subject experiences an unacceptable toxicity that precludes continuation in the study, as agreed by the Investigator and the Sponsor.
- Lack of recovery from a DLT to Grade 0 or 1 within 14 days of occurrence.
- Female patient becomes pregnant.
- Disease progression.

4.7 Randomisation

This is a non-randomized study.

4.8 Blinding

This is an open-label study and consequently there are no blinding procedures in operation.

4.9 Sample Size

Run-in prior to commencing dosing of BGB324 in combination with erlotinib, the safety and tolerability of single agent BGB324 will be assessed in a minimum of 6 patients. The safety data from the first cycle in these 6 patients will be reviewed by the safety monitoring committee (SMC) before enrolment into Arm A can commence.

Arm A will utilize a conventional algorithm 3+3 dose escalation algorithm for phase I cancer trials (3+3 patients per dose level) to identify the dose of BGB324 that can be safely given in

combination with erlotinib. Escalation between dose levels will occur if 0/3 or 1/6 patients experiences a DLT. Under this design, there is a 71% chance of escalation if the true but unknown rate of DLT is 20% and <50% chance of escalation if the true but unknown rate of DLT is >30%. The operating characteristics of this 3+3 design are outlined in.

Table 3: Operating Characteristics of the 3+3 Study Design

True but Unknown Rate of DLT (%)	Probability of Escalation (%)
20	71
30	49
40	31
50	17
60	8

It is anticipated that a maximum of three BGB324 dose levels will be evaluated, with up to approximately 18 patients enrolled. The total sample size in Arm A will depend upon whether DLT(s) is experienced at a given dose level (i.e., whether 3 or 6 patients have been treated) and how many dose levels are tested in order to reach the dose that can be safely administered in combination with erlotinib.

5.1 Planned Analyses

Disposition analyses will be carried out using the Enrolled Population. Demographic and baseline characteristics analyses will be carried out using the Safety Population. Safety analyses will be carried out using the Safety Analysis Population. Efficacy analyses will be carried out using the Efficacy Population.

Summary statistics will be presented for continuous variables, by way of n, mean, standard deviation (SD), median, minimum (Min) and maximum (Max) and by way of group frequencies and percentages for categories of categorical variables. No statistical comparison of dose levels will be performed. Percentages will be calculated using the total subjects per dose cohort in the given population unless otherwise noted.

All data from this study will be presented in data listings. Unless otherwise noted, listings will be sorted by cohort dose level and subject.

Baseline is the most recent assessment prior to the first dose of a study drug (BGB324 or erlotinib) administration, i.e within 28 days before the first dose of study drug and after patient eligibility has been confirmed. Typically, this will be Cycle 1 Day 1 or screening. Where calculated, absolute change from baseline will be presented using the following formula for each parameter: Value at the visit/timepoint – value at baseline.

Data will be presented by dose/cohort and overall.

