4.1 Discussion of Study Design

This is a multi-center open-label Phase 1/2 study of BGB324 as a single agent (Run-in Cohort) and in combination with erlotinib (Arms A, B and C) in patients with Stage IIIb or Stage IV NSCLC.

At time of amendment 5, patient recruitment into the Run-In cohort (BGB324 monotherapy) and Arm A (BGB324 dose escalation in combination with erlotinib) has completed and the RP2D has been confirmed. Patients that remain on treatment in the Run-In cohort or Arm A must be followed up in accordance with the protocol schedule.

This study is anticipated to be conducted at approximately 10 sites in the US and in Europe (the number of sites and the involvement of European sites may be revised to reflect changes in recruitment rates), and will enroll up to approximately 60 patients with histologically- or cytologically-confirmed Stage IIIb or Stage IV NSCLC.

It is anticipated that up to six patients will be enrolled in the Run-in Cohort, 18 patients in Arm A, up to 25 patients in Arm B, and up to 14 patients in Arm C. Recruitment into Arm C may be stopped if Arm B completes recruitment or is stopped before the 14 patient target is reached. Patients already enrolled into Arm C at that time will be allowed to continue in the study in accordance with the protocol.

Prior to starting dosing of BGB324 in combination with erlotinib, the safety and tolerability of single agent BGB324 will be assessed in the Run-in Cohort (Phase 1) in patients who have either exhausted existing licensed therapies or are unsuitable for existing licensed therapies

for NSCLC. A minimum of 6 patients must each receive at least 1 continuous 21-day cycle of BGB324 before enrolment into Arm A can commence.

Arm A (Phase 1) incorporates a standard 3+3 design to determine the dose of BGB324 that can be safely administered in combination with erlotinib in patients who have received prior treatment with erlotinib. To confirm the RP2D for Arms B and C, loading dose schedules, loading doses and daily dose levels will be explored in Arm A. Dosing schedules will be revised in response to reported toxicities, DLT experience and SMC recommendations (Table 4 of the protocol).

When the RP2D dose of BGB324 is identified and the dose of erlotinib to be administered in combination with BGB324 is confirmed, the Phase 2 part of the study will start and Arms B and C will open simultaneously to enrolment.

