Arm B will incorporate a two-stage design to evaluate the safety and tolerability, pharmacokinetics, pharmacodynamics and clinical activity of BGB324 in combination with erlotinib in patients with an activating EGFR mutation (including exon 19 deletion or exon 21 [L858R] substitution or other rearrangement of the EGFR gene) who are T790M negative and who have progressed after receiving treatment with an approved EGFR inhibitor (i.e. erlotinib, afatinib or gefitinib). Patients who have previously been treated with a T790M inhibitor (i.e. osimertinib) and who subsequently progressed will not require T790M testing.

Arm C will evaluate the safety and tolerability, PD and clinical activity (time to progression) of BGB324 when administered in combination with erlotinib in patients with an activating EGFR mutation (including exon 19 deletion or exon 21 [L858R] substitution or rearrangement of the EGFR gene mutation) who have received ≥ 12 weeks treatment with erlotinib without disease progression.

In all parts of the study, BGB324 will be self-administered orally according to a daily schedule during continuous 21-day treatment cycles.

[figure not shown]
Erlotinib will be self-administered orally according to a daily schedule during continuous 21-day treatment cycles (Arms A, B and C only).

Both drugs will be taken with water in the morning. BGB324 should be administered in the hour following erlotinib administration and at least 2 hours before breakfast.

Patients will be allowed to continue BGB324 treatment (as a single agent or in combination with erlotinib) if, in the opinion of the Investigator, they continue to derive clinical benefit or until unacceptable toxicity, disease progression, death or withdrawal of consent. Patients who stop BGB324 treatment will be withdrawn from the study.

An outline of the study design is provided in Figure 1.

Phase I- BGB324 Monotherapy and BGB324 Dose Escalation

Phase II- BGB324 in Combination with Erlotinib

[figure not shown]

Figure 1: BGB004 study Design Outline

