4.5.2 Safety Population

The Safety Population will be defined as all enrolled patients who receive at least one dose of BGB324 or Erlotinib.

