5.8.1.1 Subsets

- Related (BGB324) adverse events will be presented by treatment, system organ class and preferred term.
- Related (Erlotinib) adverse events will be presented by treatment, system organ class and preferred term. (Arm A, Arm B and Arm C).
- Serious adverse events will be presented by treatment, system organ class and preferred term as:
 - Related (BGB324) serious adverse events will be presented by treatment, system organ class and preferred term.
 - Related (Erlotinib) serious adverse events will be presented by treatment, system organ class and preferred term.
 - Serious adverse events will be presented by treatment group, system organ class, preferred term, and maximum CTCAE grade.
- Adverse events leading to discontinuation will be presented by treatment group, system organ class and preferred term.

- Adverse events \geq Grade 3 will be presented by treatment group, system organ class and preferred term.
- The most frequent MedDRA preferred terms ($\geq 10\%$ subjects in the overall safety population) and system organ class will be presented by treatment group.
- Separate listings will be produced for DLTs, SAEs, related AEs, discontinuations due to AEs, and events of \geq Grade 3 severity.

All other information collected (e.g. action taken) will be listed as appropriate.

Notes:

- AEs coded using MedDRA version 17.0 or above.

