5.8.4 Eastern Cooperative Oncology Group

ECOG performance status will be summarized categorically at each scheduled visit with frequencies and percentage.

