5.8.5 Electrocardiograms

Twelve-lead ECG triplicate will be collected the mean of the values will be analysed. In case, only one assessment is collected this value will be considered, if 2 or 3 assessments are performed the mean of available should be calculated.

The quantitative ECG assessments (PR interval (ms), RR interval (ms), QRS Duration (ms), QT interval (ms), and QTcF interval (ms)) will be summarized for actual values and change from Baseline to each visit/timepoint will be also presented.

ECG overall interpretation (normal, abnormal not clinically significant and abnormal clinically significant) will be presented as a categorical summary by treatment groups and scheduled visit.

Any post-baseline new or worsened echocardiogram findings during the safety evaluation period will be recorded as AEs and summarized in terms of AEs as described in [Section 5.8.1](#).

All echocardiogram data, including MUGA scan results will be presented in a data listing.

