5.12 Missing Values – Missing Visits

Missing, unused and spurious data will be considered missing at random and dealt with as such. There is no intention to implement any procedure for replacing missing data.

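### The default denominator in SAP 5.1 makes the by-visit ECOG and ECG-interpretation percentages shrink as patients leave the study

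*SAP*

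**What the plan says.** SAP 5.1 gives one rule for percentages in all tables: "Percentages will be calculated using the total subjects per dose cohort in the given population unless otherwise noted". For safety tables the population is the Safety Population, which SAP 4.5.2 defines as "all enrolled patients who receive at least one dose of BGB324 or Erlotinib". Membership depends on having been dosed once, not on still being under observation at a given visit.

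Two safety outputs are categorical and by visit:

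- SAP 5.8.4: "ECOG performance status will be summarized categorically at each scheduled visit with frequencies and percentage".
- SAP 5.8.5, on the ECG overall interpretation (normal, or abnormal split by clinical significance): "will be presented as a categorical summary by treatment groups and scheduled visit".

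Neither section names another denominator or a category for patients not assessed. SAP 5.12 adds: "There is no intention to implement any procedure for replacing missing data".

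The design ensures that numbers fall over time. SAP 4.1 states: "Patients who stop BGB324 treatment will be withdrawn from the study". SAP 4.6 makes disease progression a reason for mandatory discontinuation. Protocol 10.1.7 also leaves ECOG status off the list of assessments after 12 months, so even a patient still on treatment may have no ECOG value at late visits.

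**The concern.** A percentage at a visit is normally read as the share of patients seen at that visit. Under the default rule it is the share of everyone ever dosed in the cohort. The two agree only while nobody has left and nobody has missed the assessment. After that, the column of percentages mixes the abnormality rate with retention, and a steady rate looks like an improving one.

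Safety and tolerability is the primary objective of the Run-in Cohort and of Arms B and C. SAP 5.8 plans no formal analysis of safety data, so the descriptive tables are the safety result. ECG findings matter in particular: Protocol 6.2.3 models a mean QTcF increase of 54.3 ms at the anticipated plasma concentration, and Protocol 11.3.1.3 has its own dose-modification table for QTc prolongation.

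**Working it through.** The plan states no figure to reproduce here. The check is what the written rule does to a by-visit percentage.

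**Inputs from the documents**

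- Denominator: all subjects in the cohort within the Safety Population (SAP 5.1, 4.5.2).
- Cohort size for the illustration: N = 25, the Arm B maximum. SAP 4.1 anticipates that "up to six patients will be enrolled in the Run-in Cohort, 18 patients in Arm A, up to 25 patients in Arm B".

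**Assumed inputs (the documents give no values)**

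- Patients assessed at a visit, n: 20, 15, 10 or 5 of the 25, that is 80%, 60%, 40% or 20% remaining.
- True rate of the finding among patients assessed: constant at 40%.

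**Formula**

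With x patients showing the finding among n assessed, the rate among those assessed is x/n. The table shows x/N = (x/n) × (n/N). The factor n/N is the same for every category in the table, so the displayed categories add to n/N and not to 1.

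**Results**

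| Assessed n | n/N | With finding x | x/n | Shown, x/25 | All other categories, shown | Sum shown |
|---|---|---|---|---|---|---|
| 25 | 1.00 | 10 | 40% | 40% | 15/25 = 60% | 100% |
| 20 | 0.80 | 8 | 40% | 32% | 12/25 = 48% | 80% |
| 15 | 0.60 | 6 | 40% | 24% | 9/25 = 36% | 60% |
| 10 | 0.40 | 4 | 40% | 16% | 6/25 = 24% | 40% |
| 5 | 0.20 | 2 | 40% | 8% | 3/25 = 12% | 20% |

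The rate among those assessed never moves, yet the displayed rate falls from 40% to 8%.

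**Which outputs are affected**

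- Affected: the by-visit ECOG table (14.3.6.3.1) and the ECG overall-interpretation table (14.3.6.2.2).
- Not affected: continuous by-visit summaries of ECG intervals, vital signs and laboratory values. SAP 5.1 lists n among their statistics, and means and medians use available values.
- Not affected: adverse event incidence. That is cumulative over treatment, and everyone dosed in the cohort is the right denominator.
- QTcF also has tables by CTCAE grade and of maximum increase (14.3.6.2.3 and 14.3.6.2.4), whose titles are not by visit.

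**The case against.** The best defence is that nothing is lost. Counts are printed beside percentages (SAP 5.8.4 and the conventions in SAP 6.2), so the category counts add to the number assessed. Table 14.1.7.3 gives participants by cycle. In the n = 10 row above, a reader would see 4 (16.0%) beside counts totalling 10 and could work out 40%. SAP 5.1 is also only a default, and a table shell could state another denominator. All of this stands, and it limits the harm. It does not remove the problem: the SAP text makes no exception, and a reader should not have to rebuild a percentage to learn the rate.

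Two stronger readings are tempting, and the documents do not support them.

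- A reader might infer that departed patients are counted as not abnormal. They are in no category. The percentage normal shrinks by the same factor as the percentage abnormal, and the shortfall from 100% is visible.
- A reader might infer a second dilution from SAP 5.8.1.1, where the most frequent terms are those reaching 10% of "subjects in the overall safety population) and system organ class will be presented by treatment group". That cut-off changes no percentage. It selects rows for Table 14.3.1.6.1, while the tables without a frequency cut (14.3.1.2.1 to 14.3.1.2.5 and others) show every term, and SAP 5.1 has data presented by cohort and overall. An event seen only in 6 Arm B patients is dropped if all arms fill (6 + 18 + 25 + 14 = 63; 6/63 = 9.5%), but kept at the stated total of about 60 (6/60 = 10.0%). At 63, one further case in any other arm also keeps it (7/63 = 11.1%). Switching to 10% in any arm would admit every single Run-in event (1/6 = 16.7%). The pooled cut-off is a display preference, not an error.

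**Conclusion.** The point holds for two tables. Followed as written, the SAP shrinks every by-visit percentage of ECOG status and ECG interpretation by the fraction of the cohort assessed, so drop-out alone can look like improvement. The size depends entirely on retention, which the documents do not give: at an assumed 80% to 20% assessed, displayed percentages are 0.8 to 0.2 times the rate among those assessed. The 40% rate and N = 25 are illustrative; the factor n/N applies whatever the rate or cohort size.

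No hypothesis test, DLT evaluation, dose decision or adverse event percentage changes, and the correct rate can be recovered from the counts. It is a modest defect in how a primary-objective domain is displayed, and worth correcting because the correction is so cheap.

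**What to change.** Add one sentence to SAP 5.1: *For by-visit categorical tables the denominator is the number of patients in the cohort with a non-missing assessment at that visit, and this n is shown.* Leave the full-cohort denominator in place for adverse event incidence, and leave the 10% cut-off in SAP 5.8.1.1 as it is.

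Showing n matters as much as changing the denominator. The new percentage describes only patients still under assessment, who may differ from those who left, and the reader needs n to judge that.

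The cost is one sentence of SAP text and the matching denominator in two table programs. No new data are needed and the protocol does not change.
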